8.2.3.2 Pulse Oximetry

Oxygen saturation will be measured using a standard pulse oximeter. The subject must be in a rested and calm state for at least 5 minutes before pulse oximetry assessments are completed. After each AMG 910 infusion for the first 2 cycles and after the first 2 infusions of cycle 3 **and after start of eIV infusion on cycle 1 day 1**, but only while the patient is hospitalized or under observation post AMG 910 infusions, pulse oximetry should be assessed accordingly during the following timepoints:

Short-term IV Infusion:

- Every 15 minutes during infusion and during first 2 hours after end of infusion (EOI)
- Every 30 minutes from 2 to 4 hours after EOI
- Every hour from 4 to 8 hours after EOI
- Every 2 hours from 8 to 12 hours after EOI
- Every 6 hours from 12 to 24 hours after EOI
- After 24 hours EOI, pulse oximetry should be assessed per institutional standards

Extended IV infusion:

- **15 minutes after start of eIV infusion**
- **every 30 minutes thereafter during the first 2 hours after start of eIV infusion**
- **every 1 hour during hours 3 to 6 after start of eIV infusion**
- **every 2 hours during hours 7 to 12 after start of eIV infusion**
- **every 6 hours during hours 13 to 24 after start of eIV infusion**
- **after 24 hours after start of eIV infusion vital signs should be assessed per institutional standards**

8.2.3.3 Electrocardiograms (ECGs)

Subject must be in supine position in a rested and calm state for at least 5 minutes before ECG assessment is conducted. If the subject is unable to be in the supine position, the subject should be in most recumbent position as possible. ECGs should be performed in a standardized method, in triplicate, and run consecutively (all 3 ECGs should be completed within a total of five minutes from the start of the first to the completion of the third), prior to blood draws or other invasive procedures. If it is necessary to schedule blood draws for the predose timepoints (see Section 1.3, Schedule of Activities) before the ECG to allow for timely administration of investigational product, blood draws should be performed at least 60 minutes before the ECG. Each ECG must include the following measurements: QRS, QT, QTc, RR, and PR intervals.

- For screening: triplicate ECGs
- For cycle 1: ≥ 3 baseline ECGs collected ≥ 30 minutes apart, with each baseline ECG in triplicate run consecutively (all 3 ECGs should be completed within a total of five minutes from the start of the first to the completion of the third) (total 9 ECGs)

- For cycle 1: triplicate ECGs at time points after dosing
- For cycle 2 and beyond: single ECGs may be collected per time point

Baseline is defined as the pre-dose assessment on cycle 1 day 1. The investigator or designated site clinician will review all ECGs. **Electrocardiograms** may be transferred electronically to an ECG central reader for analysis per Amgen instructions. Once signed, the original ECG tracing will be retained with the subject's source documents. At the request of the sponsor, a copy of the original ECG will be made available to Amgen. Standard ECG machines should be used for all study-related ECG requirements.

8.2.3.4 Vital Status

Vital status must be obtained for all subjects within the limits of local law. This includes subjects who may have discontinued study visits with or without withdrawing consent and should include interrogation of public databases, if necessary. If deceased, the date and reported cause of death should be obtained.

8.2.4 Adverse Events and Serious Adverse Events

8.2.4.1 Time Period and Frequency for Collecting and Reporting Safety Event Information

8.2.4.1.1 Adverse Events

The adverse event grading scale to be used for this study will be the Common Terminology Criteria for Adverse Events (CTCAE) version 5.0 and is described in Section 11.14, with the exception of CRS, which will be graded using the criteria referenced in the publication by Lee et al (2014) (see Section 11.13) and TLS, which will be graded according to the Cairo Bishop criteria referenced in the publication by Coiffier et al (2008) (see Section 11.14).

The investigator is responsible for ensuring that all adverse events observed by the investigator or reported by the subject that occur after first dose of investigational product(s)/study treatment/protocol-required therapies through the safety follow-up visit (30 [+3] days after the last dose of investigational product/study treatment/protocol-required therapies) are reported using the Events CRF.

8.2.4.1.2 Serious Adverse Events

The investigator is responsible for ensuring that all serious adverse events observed by the investigator or reported by the subject that occur after signing of the informed

consent through the **LTFU visit or End of Study Visit (whichever occurs later)** are reported using the **Events** CRF.

All serious adverse events will be collected, recorded, and reported to the sponsor or designee within 24 hours of the investigator's knowledge of the event, as indicated in Section 11.4. The investigator will submit any updated serious adverse event data to the sponsor within 24 hours of it being available.

The criteria for grade 4 in the CTCAE grading scale differs from the regulatory criteria for serious adverse events. It is left to the investigator's judgment to report these grade 4 abnormalities as serious adverse events.

8.2.4.1.3 Serious Adverse Events After the Protocol-required Reporting Period

There is no requirement to monitor study subjects for serious adverse events following the protocol-required reporting period (**as defined in Section 8.2.4.1.2**) or after end of study. However, these serious adverse events **should** be reported to Amgen (**regardless of causality**) if the investigator becomes aware of them. Per local requirements in some countries, investigators are required to report serious adverse events that they become aware of after end of study. If serious adverse events are reported, the investigator is to report them to Amgen within 24 hours following the investigator's knowledge of the event.

Serious adverse events reported outside of the protocol-required reporting period will be captured within the safety database as clinical trial cases and handled accordingly based on relationship to investigational product.

The method of recording, evaluating, and assessing causality of adverse events and serious adverse events and the procedures for completing and transmitting serious adverse event reports are provided in Section 11.4.

8.2.4.1.4 Reporting a Safety Endpoint as a Study Endpoint

Safety endpoints that are study endpoints are reported on the **Events** CRF. All endpoints that also meet the criteria of serious adverse event must also be transmitted to safety within 24 hours of the investigator's knowledge of the event (refer to Section 11.4).

8.2.4.2 Method of Detecting Adverse Events and Serious Adverse Events

Care will be taken not to introduce bias when detecting adverse events and/or serious adverse events. Open-ended and non-leading verbal questioning of the subject is the preferred method to inquire about adverse event occurrence.

8.2.4.3 Follow-up of Adverse Events and Serious Adverse Events

After the initial adverse event/serious adverse event report, the investigator is required to proactively follow each subject at subsequent visits/contacts. All adverse events and serious adverse events will be followed until resolution, stabilization, until the event is otherwise explained, or the subject is lost to follow-up (as defined in Section 7.3).

Further information on follow-up procedures is given in Section 11.4.

All new information for previously reported serious adverse events must be sent to Amgen within 24 hours following knowledge of the new information. If specifically requested, the investigator may need to provide additional follow-up information, such as discharge summaries, medical records, or extracts from the medical records.

Information provided about the serious adverse event must be consistent with that recorded on the Events CRF.

8.2.4.4 Regulatory Reporting Requirements for Serious Adverse Events

If subject is permanently withdrawn from protocol-required therapies because of a serious adverse event, this information must be submitted to Amgen.

Prompt notification by the investigator to the sponsor of serious adverse events is essential so that legal obligations and ethical responsibilities towards the safety of subjects and the safety of a study treatment under clinical investigation are met.

The sponsor has a legal responsibility to notify both the local regulatory authority and other regulatory agencies about the safety of a study treatment under clinical investigation. The sponsor will comply with country-specific regulatory requirements relating to safety reporting to the regulatory authority, IRBs/IECs, and investigators.

Individual safety reports must be prepared for suspected unexpected serious adverse reactions according to local regulatory requirements and sponsor policy and forwarded to investigators as necessary.

An investigator who receives an individual safety report describing a serious adverse event or other specific safety information (eg, summary or listing of serious adverse events) from the sponsor will file it along with the Investigator's Brochure and will notify the IRB/IEC, if appropriate according to local requirements.

8.2.4.5 Safety Monitoring Plan

Subject safety will be routinely monitored as defined in Amgen's safety surveillance and signal management processes.

8.2.4.6 Pregnancy and Lactation

Details of all pregnancies and/or lactation in female subjects will be collected after the start of study treatment and until 75 days after the last dose of AMG 910 or in a male subject's female partner through 5 months after the last dose of AMG 910.

If a pregnancy is reported, the investigator is to inform Amgen within 24 hours of learning of the pregnancy and/or lactation and is to follow the procedures outlined in Section 11.5. Amgen Global Patient Safety will follow-up with the investigator regarding additional information that may be requested.

Abnormal pregnancy outcomes (eg, spontaneous abortion, fetal death, stillbirth, congenital anomalies, ectopic pregnancy) are considered serious adverse events.

Further details regarding pregnancy and lactation are provided in Section 11.5.

8.2.5 Clinical Laboratory Assessments

Refer to Section 11.2 for the list of clinical laboratory tests to be performed and to the Schedule of Activities (Table 1-1) for the timing and frequency.

The investigator is responsible for reviewing laboratory test results and recording any clinically relevant changes occurring during the study in the Events CRF. The investigator must determine whether an abnormal value in an individual study subject represents a clinically significant change from the subject's baseline values. In general, abnormal laboratory findings without clinical significance (based on the investigator's judgment) are not to be recorded as adverse events. However, laboratory value changes that require treatment or adjustment in current therapy are considered adverse events. Where applicable, clinical sequelae (not the laboratory abnormality) are to be recorded as the adverse event.

All protocol-required laboratory assessments, as defined in Section 11.2, must be conducted in accordance with the laboratory manual and the Schedule of Activities (Table 1-1).

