6.2.1.3 Dose-limiting Toxicity

The adverse event grading scale to be used for this study will be the CTCAE version 5.0 and is described in Section 11.4, with the exception of CRS, which will be graded using

the criteria referenced in the publication by Lee et al (2014) (see Section 11.13) and TLS, which will be graded according to the Cairo Bishop criteria referenced in the publication by Coiffier et al (2008) (see Section 11.14).

Dose-limiting toxicities are defined as any adverse events at least possibly related to AMG 910 with an onset within the first 28 days following first dose for single-subject cohorts and within the safety observation period for multiple-subject cohorts as defined in Section 6.2.1.1.2 with any of the following criteria:

- grade 2 gastric perforation or fistula
- grade ≥ 3 non-hematologic adverse events including laboratory abnormalities with the exceptions as stated below:
 - grade 3 fever (not associated with any other CRS/**infusion-related reaction** symptoms) that does improve to grade ≤ 1 within 72 hours
 - grade 3 nausea, vomiting, or diarrhea that does improve to grade ≤ 1 or baseline within 72 hours with optimal medical support.
 - grade 3 asymptomatic liver enzyme elevations including AST, ALT, GGT with AST improving to grade ≤ 2 within 72 hours and ALT and GGT, which have long half-lives, improving to grade ≤ 2 within 7 days except those meeting Hy's Law
- re-challenge with AMG 910 after treatment interruption due to any stomach toxicity results in at least same stomach toxicity and is of CTCAE grade ≥ 3 or grade 2 and ongoing for more than 3 days despite optimal supportive treatment
- grade 4 thrombocytopenia or grade 3 thrombocytopenia with bleeding
- grade 4 neutropenia lasting longer than 28 days
- febrile neutropenia of any grade
- anemia requiring transfusion per local or international guidelines in the absence of bleeding
- grade 5 toxicity (eg, death not due to disease progression)
- any other toxicity related to AMG 910 considered significant enough to be qualified as DLT in the opinion of the investigator, and confirmed by the DLRT, will be reported as DLT

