6.2.2.3.2 Infusion Interruptions due to Adverse Events

Events occurring during the infusion and requiring treatment interruption will be managed by immediate infusion interruption. The site should record any unscheduled interruption of an infusion on the electronic CRF (eCRF) and provide the start and stop date/time of the infusion.

Events requiring an infusion interruption are listed in [Table 6-3](#).

For eIV infusions, the following adverse events should not lead to infusion interruption or delayed dosing of a next scheduled dose:

- **grade 1 or 2 CRS (including transient fever and/or vomiting [< 72 hours])**
- **grade 3 transaminitis**
- **grade 3 hypotension manageable with IV fluids or low dose vasopressor**
- **grade 3 or 4 lymphopenia resolving to grade ≤ 2 within 7 days or considered not clinically relevant**
- **isolated grade 3 fever (defined as a temperature $\geq 40^{\circ}\text{C}$ with a duration of ≤ 24 hours) occurring outside the context of CRS**
- **laboratory parameters of grade ≥ 3 , not considered clinically relevant**
- **hemoglobin ≥ 7.0 to < 8.0 g/dL if observed ≤ 7 days in the absence of bleeding signs**

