
• Any abnormal laboratory test results (hematology, clinical chemistry, or urinalysis) or other safety assessments (eg, electrocardiogram, radiological scans, vital signs measurements), including those that worsen from baseline, that are considered clinically significant in the medical and scientific judgment of the investigator (ie, not related to progression of underlying disease).• Exacerbation of a chronic or intermittent pre-existing condition including either an increase in frequency and/or intensity of the condition.• New conditions detected or diagnosed after study treatment administration even though it may have been present before the start of the study.• Signs, symptoms, or the clinical sequelae of a suspected drug-drug interaction.• Signs, symptoms, or the clinical sequelae of a suspected overdose of either study treatment or a concomitant medication. Overdose per se will not be reported as an adverse event/serious adverse event unless it is an intentional overdose taken with possible suicidal/self-harming intent. Such overdoses are to be reported regardless of sequelae.• For situations when an adverse event or serious adverse event is due to gastric cancer, report all known signs and symptoms. Death due to disease progression in the absence of signs and symptoms should be reported as the primary tumor type (eg, metastatic pancreatic cancer). Note: The term “disease progression” should not be used to describe the adverse event.• “Lack of efficacy” or “failure of expected pharmacological action” per se will not be reported as an adverse event or serious adverse event. Such instances will be captured in the efficacy assessments. However, the signs, symptoms, and/or clinical sequelae resulting from lack of efficacy will be reported as adverse event or serious adverse event if they fulfill the definition of an adverse event or serious adverse event.

Events NOT Meeting the Adverse Event Definition

- Medical or surgical procedure (eg, endoscopy, appendectomy): the condition that leads to the procedure is the adverse event.
- Situations in which an untoward medical occurrence did not occur (social and/or convenience admission to a hospital).
- Anticipated day-to-day fluctuations of pre-existing disease(s) or condition(s) present or detected at the start of the study that do not worsen.

Definition of Serious Adverse Event

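### Sections 8.2.5 and Appendix 4 can keep a laboratory finding off the adverse-event record that Section 6.2.1.3 counts as a DLT, and nothing in the plan reconciles the two

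*Protocol*

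**What the plan says.** **What gets recorded.** Protocol 8.2.5 states that "abnormal laboratory findings without clinical significance (based on the investigator's judgment) are not to be recorded as adverse events". The sentence opens with a qualifier marking it as the general case, and the next adds that "laboratory value changes that require treatment or adjustment in current therapy are considered adverse events". It then says, where applicable, that "clinical sequelae (not the laboratory abnormality) are to be recorded as the adverse event". The adverse-event definition in Protocol Appendix 4 has the same filter: abnormal results count if they are ones "that are considered clinically significant in the medical and scientific judgment of the investigator".

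**What counts as a DLT.** Protocol 6.2.1.3 begins: "Dose-limiting toxicities are defined as any adverse events at least possibly related to AMG 910". Among the criteria are grade 3 or higher "non-hematologic adverse events including laboratory abnormalities with the exceptions as stated below". The only laboratory exception is for asymptomatic grade 3 liver enzymes that improve within set times. No exception refers to judged clinical significance. A separate criterion is "grade 4 thrombocytopenia or grade 3 thrombocytopenia with bleeding".

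**A third place.** Protocol 6.2.2.3.2, on extended infusions, says "the following adverse events should not lead to infusion interruption or delayed dosing of a next scheduled dose". The list that follows includes laboratory parameters of grade 3 or higher considered not clinically relevant. That section therefore calls such values adverse events.

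**How the record is used.** Under SAP 6.3.1 a subject without a DLT in the window is evaluable and enters as a non-DLT. Protocol 9.4.2.3.1 and SAP 9.6.1 estimate the DLT probability by dose with the two-parameter BLRM.

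**The concern.** A value must be an adverse event before it can be a DLT, and 8.2.5 with Appendix 4 lets an investigator decide that a grade 3 or higher value is not one. There are two routes to loss:

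- **Judgment.** An untreated, isolated grade 3 or 4 chemistry value is called not clinically significant and is not entered.
- **Substitution.** A subject with grade 3 thrombocytopenia and grade 1 bleeding is entered, on a literal reading of 8.2.5, as grade 1 bleeding. The pair is a named DLT. The investigator need not have misjudged significance for this to happen.

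DLT is the first-listed primary endpoint and the outcome the BLRM models. A lost event becomes a non-DLT rather than a missing value, so any loss lowers the DLT count. With approximately 30 sites and cohorts of 3 to 4, identical values can be classified differently, and one event carries weight. In expansion, the stopping rule counts grade 4 or higher treatment-related adverse events (Protocol 9.4.1.1), so untreated grade 4 laboratory values pass through the same filter.

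**Working it through.** **1. The passages side by side**

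| Finding in the DLT window, at least possibly related | Under 6.2.1.3 | Under 8.2.5 / Appendix 4 |
|---|---|---|
| Grade ≥3 chemistry value, treated | DLT unless a listed exception applies | Adverse event: no conflict |
| Grade ≥3 chemistry value, untreated, judged not significant, no listed exception | DLT | By default not recorded |
| Grade 3 thrombocytopenia with grade 1 bleeding | DLT | Sequela recorded, at its own grade |
| Anemia needing transfusion | DLT (absent bleeding) | Adverse event, because treated: no conflict |

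The conflict lies in the second and third rows.

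**2. The plan's own figures.** Protocol 9.2 gives the chance of at least one DLT, 1 − (1 − p)^n, for p = 10% to 33%. Recomputed: 27.1% to 69.9% for n = 3 and 34.4% to 79.8% for n = 4, matching the stated 27% to 70% and 34% to 80%.

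**3. If a share s of true DLTs goes unrecorded** (assumption; the documents give no value), replace p by p(1 − s). At a true rate of 33%:

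| s | n = 3 | n = 4 |
|---|---|---|
| 0% | 69.9% | 79.8% |
| 10% | 65.3% | 75.6% |
| 20% | 60.1% | 70.7% |
| 30% | 54.5% | 65.0% |
| 50% | 41.8% | 51.4% |

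A true rate of 40% with s = 20% is seen as 0.40 × 0.80 = 32%, inside the 20% to 33% target interval.

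**4. One lost event in the BLRM.** The model form assumed is logit(p) = ln a + b·ln(dose/3500), with the Appendix 9 prior: ln a of mean −0.847 and SD 1.275, ln b of mean −1.098 and SD 1.981, correlation 0. It reproduces the stated prior checks:

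- p at 6.5 µg at the prior means = 0.050 (stated 0.05).
- P(p ≤ 0.40 at 6.5 µg) = 0.896 (stated 0.90).
- P(p ≤ 0.05 at 3500 µg) = 0.050 (stated 0.05).

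A dose is admissible if P(DLT rate > 33%) is below 0.40. By grid integration, with data at 6.5 µg only:

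| Data at 6.5 µg | P(over) 2.5 µg | P(over) 6.5 µg | P(over) 15 µg | Result |
|---|---|---|---|---|
| 2 DLTs in 3 | 0.644 | 0.678 | 0.708 | No admissible dose |
| 1 DLT in 3 | 0.269 | 0.298 | 0.328 | 15 µg admissible |

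The next-level cap in Protocol 6.2.1.1.2 permits 15 µg after 6.5 µg, so here one unrecorded event changes what the model allows as the next step.

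**5. Expansion.** The boundary at 10 subjects is 4 or more events. With the stated Beta(0.40, 1.60) prior, 4 events give posterior Beta(4.4, 7.6) and P(rate > 20%) = 0.895, above the 0.80 limit. Three recorded events give Beta(3.4, 8.6) and 0.719, below it. One unrecorded grade 4 value can therefore leave the boundary uncrossed.

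**The case against.** **Qualifiers.** Both sentences in 8.2.5 are hedged, treated values are adverse events, and a general default need not override a specific DLT criterion. Under Appendix 7, qualifying AST or ALT elevations concurrent with raised bilirubin and/or INR must be reported as serious adverse events within 24 hours. This stands. It confines the gap to the two rows above, but does not say which section governs there.

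**Safeguards.** The DLRT reviews laboratory results and the data are queried (Appendix 3). After a first DLT, laboratory data are weighed beside the BLRM recommendation (6.2.1.1.2). Escalation needs a unanimous vote, and SAP 9.6.3 tabulates laboratory grade shifts. These may catch cases. None requires a value to be checked against 6.2.1.3 or entered in the BLRM, and the catch-all DLT criterion starts from the investigator's opinion that the toxicity is significant.

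**The liver-enzyme exception.** A reader might infer that it would be redundant if asymptomatic values were not adverse events. That does not follow: an asymptomatic elevation can still be clinically significant, so the exception keeps a purpose under 8.2.5.

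**Large dose shifts.** A reader might infer that one lost event moves the dose a long way. With no DLT in 8 subjects at 6.5 µg or in 4 each at 15, 30 and 60 µg, 2/4 DLTs at 150 µg ranks 600 µg highest, and 1/4 ranks 2000 µg highest. This is a model ranking only. The next-level cap allows at most 300 µg, admissible either way (P(over) 0.076 and 0.018), and an MTD needs 6 or more evaluable subjects already treated at the dose. No immediate trial action changes.

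**Conclusion.** The concern holds as a conflict of wording that reaches a primary endpoint. Sections 8.2.5 and Appendix 4 can keep off the adverse-event record a finding that 6.2.1.3 counts as a DLT, while 6.2.2.3.2 treats comparable values as adverse events. The gap is limited to untreated values judged not significant and to values replaced by a lower-grade sequela. Within it, any loss lowers the DLT count.

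The documents do not support the stronger inference that laboratory DLTs are excluded as a rule, or that a given share is lost; their frequency is unknown, and the 0% to 50% range is an assumption. The 6.5 µg illustration shows that one event can matter. It does not predict what would happen, and it assumes that the Appendix 9 prior carries over to the Table 6-2 doses, that no other data are used, and that the 0.40 limit applies to each next-dose choice as in the Appendix 9 simulations. Severity is moderate.

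**What to change.** 1. In Protocol 8.2.5 and Appendix 4, state that any laboratory value meeting a 6.2.1.3 criterion with onset in the DLT window is recorded on the Events CRF under its own term, grade and causality, whatever its judged significance and in addition to any sequela. Apply the same to any grade 4 value in expansion.
2. Add to the DLRT package a listing that reconciles every grade 3 or higher laboratory value in the DLT window with the recorded DLTs and gives the reason where there is no match. Since SAP 7.1 says the study is closing early, the same listing would also support the final DLT analysis.
3. If the sponsor intends values judged not significant to be exempt, write that exemption into 6.2.1.3 and bring 6.2.2.3.2 into line. The choice is the sponsor's, but the sections must agree.

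The cost is one or two sentences, one listing from data already collected, and a few more adverse-event entries.
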